4.8.3 Deaths, Serious Adverse Events, and Other Significant Adverse Events

An overview of AEs, including the number and percentage of subjects who died, reported serious adverse events (SAEs), and discontinued due to AEs will be provided. The incidence of treatment emergent SAEs will be presented by SOC, PT, and treatment group.

Listings of all SAEs and deaths as well as AEs leading to discontinuation will be provided.

4.8.4 Clinical Laboratory Evaluation

All laboratory values will be reported in International System of Units (SI). Summary displays for laboratory safety data (continuous and categorical parameters) will be produced by visit and treatment group. Summary statistics will be produced for both observed and change from baseline values of the different laboratory variables.

If there are multiple records of laboratory measurements at any post-baseline visit, the worst valid record will be used. It is noted that invalid laboratory data may not be used (from hemolyzed samples, mishandled samples, quantity not sufficient, or other conditions that would render values invalid). Missing data will be maintained as missing for all summaries.

The following laboratory variables will be determined at screening, baseline, Weeks 4 (liver function tests only), 13, 26, and 30 as indicated in the protocol and Table 2 below. It is noted that reducing substance was included in the protocol as part of the urinalysis assessments but was not performed and is not included in the summaries.

Table 2: Laboratory Assessments			
Hematology:	erythrocytes	Endocrinology:	free T4
	hemoglobin		pregnancy test ^a
	hematocrit		
	MCV		
	MCH		
	neutrophils		
	eosinophils		
	basophils		
	lymphocytes		
	monocytes		
	platelets		
	leukocytes		

Clinical chemistry:
 
 sodium potassium chloride calcium phosphorus glucose creatinine urea uric acid total bilirubin ^b direct bilirubin ^b indirect bilirubin ^b alkaline phosphatase ^b AST ^b ALT ^b GGT ^b albumin ^b total protein ^b triglycerides cholesterol calculated creatinine clearance vitamin B12 HbA1c 	
Urinalysis (macroscopy):
 
 appearance bilirubin color glucose ketone leukocytes nitrite occult blood protein reaction pH specific gravity 
Microscopy will be done if macroscopy is abnormal

---	---

ALT=alanine aminotransferase; AST=aspartate aminotransferase; GGT=gamma-glutamyl transpeptidase; HbA1c=glycated hemoglobin; MCV=mean corpuscular volume; MCH=mean corpuscular hemoglobin; T4=thyroxine.

- a. At screening and Week 26 for women of childbearing potential, a urine pregnancy test will be performed. Positive result will be confirmed by a serum pregnancy test
- b. At Week 4, only liver function tests will be performed.

Laboratory values will be classified as normal, low, or high based on normal ranges supplied by the central laboratory. A summary of shift from baseline classifications will be provided by visit and treatment group for the hematology and clinical chemistry parameters.

The number and percentage of subjects with elevated alanine aminotransferase (ALT), aspartate aminotransferase (AST), or total bilirubin, meeting any 1 of the following criteria will be summarized by treatment group for each visit and overall:

- ALT or AST $\geq 8x$ upper limit of normal (ULN)
- ALT or AST $\geq 5x$ ULN for more than 2 weeks
- ALT or AST $\geq 3x$ ULN and total bilirubin $\geq 2x$ ULN at the same visit
- ALT or AST $\geq 3x$ ULN with the appearance of symptoms indicating hepatitis (e.g., worsening fatigue, nausea, vomiting, right upper quadrant pain or tenderness, fever, rash, or eosinophilia)

Due to an equipment malfunction at the analytic laboratory, serum creatinine results for some subjects may have increased by approximately 0.3-0.4 mg/dL between October 1, 2016 and January 13, 2017. This affected both the serum creatinine results and the calculated creatinine clearance, since calculated creatinine clearance is derived from creatinine. These results will be excluded from the primary lab summaries but will be included in the listing. A second summary for serum creatinine will be presented where the values of all the affected samples are decreased by 0.35 mg/dL. No correction will be performed for calculated creatinine clearance.

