6.2.2 Laboratory Variables

Laboratory assessments will be performed by a central laboratory, as identified in the List of Study Personnel. For safety reasons, laboratory assessments may also be performed locally in case of an emergency.

Blood samples should be taken using standard venipuncture techniques. Further instructions are available in the Manual for laboratory evaluations.

The following laboratory variables will be determined at screening, baseline and Weeks 4 (liver function tests only), 13, 26 and 30 as indicated in the Schedule of Procedures ([Table 3](#)):

Table 2: Laboratory Assessments

Hematology:
 
 erythrocytes hemoglobin hematocrit MCV MCH neutrophils eosinophils basophils lymphocytes monocytes platelets leukocytes 	
Endocrinology:
 
 free T4 pregnancy test ^a

Clinical chemistry:
 
 sodium potassium chloride calcium phosphorus glucose creatinine urea uric acid total bilirubin ^b direct bilirubin ^b indirect bilirubin ^b alkaline phosphatase ^b AST ^b ALT ^b GGT ^b albumin ^b total protein ^b triglycerides cholesterol calculated creatinine clearance vitamin B12 HbA1c 	
Urinalysis (macroscopy):
 
 appearance bilirubin color glucose ketone leukocytes nitrite occult blood protein reaction pH reducing substance specific gravity 
Microscopy will be done if macroscopy is abnormal

ALT=alanine aminotransferase; AST=aspartate aminotransferase; GGT=gamma-glutamyl transpeptidase; HbA1c=glycated hemoglobin; MCV=mean corpuscular volume; MCH=mean corpuscular hemoglobin; T4=thyroxine.

a. At screening and Week 26 for women of childbearing potential, a urine pregnancy test will be performed. Positive result will be confirmed by a serum pregnancy test

b. At Week 4, only liver function tests will be performed.

All clinical laboratory test results outside of the reference range will be interpreted by the investigator using the following categories:

- Abnormal but not a clinically significant worsening

- Abnormal and a clinically significant worsening.

A laboratory test result that has significantly worsened (according to medical judgment) compared to the baseline result will be recorded on the eCRF as an AE.

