4.8.2 Adverse Events

AEs will be coded using MedDRA (Version 18.1) with reference to SOC and PT. All of the displays will be summarized by SOC and PT unless otherwise specified.

The following AE summaries will be presented by treatment group:

- Number and percentage of TEAE
- Number and percentage of treatment related TEAE

- Number and percentage of TEAE by SOC, PT, and severity
- Number and percentage of treatment related TEAE by SOC, PT, and severity
- Number and percentage of TEAE by SOC, PT, and relatedness
- Number and percentage of Serious TEAE
- Number and percentage of Serious treatment related TEAE
- Number and percentage of TEAE leading to discontinuation
- Number and percentage of TEAE with fatal outcome

All AE summaries will provide the number of subjects reporting at least 1 adverse event and the total number of events reported.

General Rules for Adverse Events

1. An AE will be considered a TEAE if it begins on or after the first study drug dosing or that worsens in severity after at least 1 dose of study drug has been administered. In case of insufficient information to determine if the event occurred before, during or after study drug dosing, the AE will be considered treatment-emergent.

The imputation method for the handling of missing or partial dates will be as follows:

Start dates

- If the day is missing, but month and year are present and the same as the month and year of the first dose of study drug, then day will be set to the same day as the start of study drug. Otherwise this will be imputed as the first day of the month
- If the month is missing, but year is present and the same as the year of the first dose of study drug, then month will be set to the same month as the start of study drug. Otherwise this will be imputed as January
- If the year is missing, the event will be considered as treatment emergent and no imputation of the date will occur

Stop dates

- If the day is missing, this will be imputed as the last day of the month
 - If the month is missing, this will be imputed as December
 - If the year is missing, the adverse event will be considered as ongoing and no imputation of the date will occur

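### The SAP treats malfunction-period creatinine and clearance as unreliable in the laboratory summaries, but has no matching rule for any adverse events recorded from them

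*SAP*

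**What the plan says.** **Laboratory side (SAP 4.8.4).** The SAP states that "serum creatinine results for some subjects may have increased by approximately 0.3-0.4 mg/dL between October 1, 2016 and January 13, 2017" because of a fault at the analytic laboratory, and that calculated clearance is affected because it is derived from creatinine. Three rules follow:

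- On the affected values in general: "These results will be excluded from the primary lab summaries but will be included in the listing".
- Creatinine is then shown a second time, after 0.35 mg/dL is taken off each affected value.
- Clearance gets no such second display: "No correction will be performed for calculated creatinine clearance".

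The same section says more generally that invalid laboratory data may not be used.

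**Route from laboratory value to AE (Protocol 6.2.1.2 and 6.2.2).** The AE definition covers abnormal laboratory findings. Under 6.2.2 a laboratory "result that has significantly worsened (according to medical judgment) compared to the baseline result will be recorded on the eCRF as an AE".

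**AE side (SAP 4.8.2 and 4.8.3).** "An AE will be considered a TEAE if it begins on or after the first study drug dosing", or if it worsens in severity after dosing. The planned tables cover all, related, serious, fatal and discontinuation TEAEs, with breakdowns by SOC, PT, severity and relatedness. A causality of not assessable, or a missing causality, counts as related. Neither section mentions the creatinine fault.

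**Routes for change.** SAP 4.3.2 plans blinded data review meetings before unblinding. SAP 4.11 lets those reviews alter planned analyses before database lock. Neither names this issue.

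**The concern.** A single reading can feed two safety displays: the laboratory summary and, if the investigator judged it a significant worsening, an AE record. The SAP deals with the first and is silent on the second. As written, a value considered too unreliable for the primary laboratory summary could still be counted, without qualification, as a treatment-emergent event, and as a related one if causality was left missing or marked not assessable.

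What is at stake is the reading of renal safety. SAP 4.7.1.3 says safety results are interpreted on clinical grounds without testing, so the reader relies on the counts and percentages themselves. Events produced by the fault would raise the absolute rates in all arms, could make a drug-placebo ratio look smaller, and with small counts could fall unevenly between arms by chance. If the decision about which AEs are artefacts is left until after unblinding, it will be open to challenge.

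**Working it through.** **1. Inputs from the documents.** Error about +0.3 to +0.4 mg/dL in some subjects, with fault dates (SAP 4.8.4). Creatinine at screening, Day 1, Day 91±2, Day 182±3 and Day 210±2; Week 4 is liver tests only (Protocol 6.2.2, Table 3). 179 subjects per arm (SAP 4.10). 1:1:1 allocation balanced by site in blocks of 6 (SAP 3.1). Not given: the number of affected samples, the number of AEs recorded from them, renal AE rates and reference ranges. Values for these are assumptions below.

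**2. The plan's own correction.** (0.3 + 0.4)/2 = 0.35 mg/dL, so the subtraction is the midpoint of the stated range and leaves a residual of up to ±0.05.

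**3. Could on-study subjects have been sampled in the window?** Length: 31 + 30 + 31 + 13 = 105 days. Longest gaps between creatinine visits: Day 1 to 93 = 92 days; Day 89 to 185 = 96; Day 179 to 212 = 33. Since 96 < 105, a subject who was on study for the whole window and kept to schedule has at least one sample in it. This does not show that the sample was affected, or how many subjects were on study then.

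**4. How large would the error look?** Apparent creatinine rise = x/c; apparent clearance fall = 1 − c/(c + x), taking clearance as inversely proportional to creatinine (assumption).

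| Assumed true creatinine c (mg/dL) | Rise for x = 0.3 to 0.4 | Clearance fall |
|---|---|---|
| 0.8 | 37.5% to 50.0% | 27.3% to 33.3% |
| 1.0 | 30.0% to 40.0% | 23.1% to 28.6% |
| 1.2 | 25.0% to 33.3% | 20.0% to 25.0% |

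Changes of this size make an AE entry plausible, not certain.

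**5. Effect of false events at an equal rate in each arm.** The fault depends on calendar time and allocation is balanced by site, so an equal rate f is a reasonable assumption. If false events are independent of true ones, the observed rate is q = p + f(1 − p). The observed difference is then (1 − f)(p1 − p0), and the ratio is q1/q0.

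| f (false events per 179) | q0, q1 for 2%, 6% | Difference (points) | Ratio, 2%/6% | Ratio, 1%/4% | Ratio, 3%/9% |
|---|---|---|---|---|---|
| 0 | 2.00%, 6.00% | 4.00 | 3.00 | 4.00 | 3.00 |
| 1% (1.8) | 2.98%, 6.94% | 3.96 | 2.33 | 2.49 | 2.50 |
| 2% (3.6) | 3.96%, 7.88% | 3.92 | 1.99 | 1.99 | 2.19 |
| 5% (9.0) | 6.90%, 10.70% | 3.80 | 1.55 | 1.48 | 1.73 |
| 10% (17.9) | 11.80%, 15.40% | 3.60 | 1.31 | 1.25 | 1.43 |

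The ratio moves a good deal; the difference loses only the fraction f of its value.

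**6. Chance imbalance with no true effect.** The 95% range of the arm difference from false events alone is ±1.96·√(2f(1 − f)/179): ±2.9 points at f = 2% and ±4.5 points at f = 5%.

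**7. The opposite direction.** If the baseline sample was inflated by 0.35 and a true rise of 0.35 followed, the two readings would be equal and no worsening would be seen. The artefact can therefore hide an event as well as create one.

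**The case against.** The strongest reply is that nothing has been shown to go wrong. The SAP says only that some results may have increased. An AE requires medical judgment. AEs are followed until, among other endpoints, the change has a satisfactory explanation (Protocol 6.2.1.6), and queries and data-handling rules exist (Protocol 9.1.1, 9.2.1, 9.4), so entries may have been corrected at source. Events coded to a creatinine term would have their own PT row, and the listings give onset dates that a reader can compare with the window. Keeping every investigator-reported AE is the conservative choice. No risk ratio is planned, and on the difference scale the effect is slight.

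Most of this stands and limits the point. It does not close the gap. No document says that AE entries were reviewed for this fault. PT rows do not repair the overall and related-TEAE totals, and matching listings by hand after unblinding does not replace a rule set beforehand.

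A reader might infer more: that the SAP simply discards the values, or that false renal events do dilute a real drug-placebo difference in every TEAE table. The documents do not support that. Creatinine returns in a corrected summary and all values stay in the listing. Neither a false AE nor a true renal difference is documented. A laboratory-only event is unlikely to reach the serious or fatal tables. The discontinuation table is reachable only through investigator discretion, because the laboratory withdrawal criteria in Protocol 6.2.2 concern ALT, AST and bilirubin.

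**Conclusion.** The inconsistency is real and modest. SAP 4.8.4 has rules for the affected values; SAP 4.8.2 has none for AEs that rest on them. Any such AEs would stay in the overall, SOC/PT, severity and relatedness tables, and possibly the discontinuation table.

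The size cannot be fixed from the documents, and the number of such AEs may be zero. Under the assumed rates, a false rate of 1% to 10% per arm takes a true ratio of 3.00 or 4.00 down to between 2.50 and 1.25 and shrinks the difference by 1% to 10% of its value. This rests on equal false rates across arms; chance imbalance or an inflated baseline could act differently. The primary endpoint and its sample size are untouched. The change is worth making because it is cheap and must be decided before unblinding to be credible.

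**What to change.** Add to SAP 4.8.2 and 4.8.4:

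- At the blinded data review, before database lock, flag each AE whose only basis is a creatinine or creatinine-clearance result from an affected sample. Identify these by sample date and a pre-listed set of preferred terms (for example creatinine increased, clearance decreased, renal impairment).
- Keep all AEs, flagged or not, in the main tables and listings.
- If any AE is flagged, repeat the overall TEAE, related TEAE and affected SOC/PT displays without the flagged AEs, and the discontinuation display if relevant, as a sensitivity display.
- If none is flagged, say so in the report.

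The cost is a paragraph of SAP text, one blinded flag and at most a few extra tables. No AE is deleted. Paired displays already have precedent in the SAP, for creatinine itself (4.8.4) and for ECGs inside and outside the timing window (4.8.5.2).

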4.8.5 Vital Signs, Physical Findings and Other Observations Related to Safety

4.8.5.1 Vital Signs

Summaries of blood pressure will be presented by visit and treatment group. Summary statistics will be produced for both observed and change values from baseline for each systolic and diastolic blood pressure.

If there are multiple records of vital sign measurements, the worst record will be used. Any repeated vital signs measurements will be excluded from summaries but included in listings. Missing data will be maintained as missing.

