8.2 General Considerations

All statistical tests will be two-sided and will be performed at the 5% level of significance, unless otherwise stated.

Continuous data will be summarized by treatment group using descriptive statistics (number, mean, median, standard deviation [SD], minimum, and maximum). Categorical data will be summarized by treatment group using frequency tables (frequencies and percent).

Analysis and data conventions:

Definition of baseline

The baseline assessment will be the latest, valid pre-dose assessment available.

Unscheduled assessments

Extra assessments (laboratory data or vital signs associated with non-protocol clinical visits or obtained in the course of investigating or managing AEs) will be included in listings, but not summaries. If more than one laboratory value is available for a given visit, the first valid observation will be used in summaries and all observations will be presented in listings. It is noted that invalid laboratory data may not be used (from hemolyzed samples, mishandled samples, quantity not sufficient, or other conditions that would render values invalid).

Missing data conventions

In general, data will not be imputed, unless stated otherwise. Imputation details will be in the SAP.

Pooling

Pooled sites will be used in the efficacy analyses. Sites with fewer than 5 subjects in any treatment group will be pooled together. Starting with the smallest site, pooling will be carried out with the next smallest site until the criteria for at least 5 subjects per treatment group have been met. If the pooled site is larger than 1.5x the largest site, pooling will be modified to create more than one pooled site. Details of the pooling will be documented prior to breaking the blind.

Outliers

Any outliers that are detected during the blind review of the data will be investigated. If necessary, queries will be issued to the Investigator, to either correct or confirm the outlier.

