4.2.1 General Definitions

Unless otherwise stated, baseline measurement is defined as the latest, valid pre-dose assessment available. 'End of Study' is defined as the last available post-treatment assessment. A subject who completes all study visits up to Week 30, will be considered to have completed the study. For evaluation of efficacy, a completed subject is defined as any subject who completes all visits up to Week 26.

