4.2.2 Visit Windows

Assessments will be classified based on the visit information reflected on the eCRF. Assessments taken outside of protocol allowable windows will be assigned based on the closest scheduled visit. If there are assessments recorded on a day that is equidistant between two visits, the assessments will be attributed to the later visit. The only exception to this rule is for assessments recorded between Baseline and Week 4. Any assessment recorded after the Baseline visit will be mapped to Week 4 even if the day is closer to the Baseline visit. The timetable of visits is given in Section 7.1 in the protocol. Nominal study visits (Weeks relative to Baseline) will be used to summarize data presented by visit.

If subjects have more than one observation for a given time point, the average of the measurements will be used. This rule applies to efficacy data. For safety data, unless otherwise specified, if there is a repeated evaluation, the worst value will be used. If values are equal, the latest repeated (latest) value will be used.

If subjects withdraw early from the study, all study assessments at the early withdrawal visit will be assigned based on the rules described above. That is, they will be assigned to the closest scheduled visit. Data from subjects who discontinue but return after 4 weeks for the follow-up visit will be summarized with the Week 30 visits.

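### The SAP's two vital-signs sentences on repeats cannot both be followed, and its worst-value rule for laboratory and ECG data sets a latest baseline against a worst follow-up value

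*SAP*

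**What the plan says.** **Blood pressure** is the only vital sign collected (Protocol 6.2.3). SAP 4.8.5.1 has two consecutive sentences: "If there are multiple records of vital sign measurements, the worst record will be used", then "Any repeated vital signs measurements will be excluded from summaries but included in listings". The general default in SAP 4.2.2 is "For safety data, unless otherwise specified, if there is a repeated evaluation, the worst value will be used".

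**Laboratory data.** Protocol 8.2: "If more than one laboratory value is available for a given visit, the first valid observation will be used in summaries". SAP 4.8.4: with several records at a post-baseline visit, "the worst valid record will be used".

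**ECG.** SAP 4.8.5.2 takes the worst result at any post-baseline visit. No other ECG-specific rule competes with it.

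**Unscheduled values.** Protocol 8.2 says that extra laboratory and vital-sign assessments, from non-protocol visits or the work-up of adverse events, "will be included in listings, but not summaries".

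**Baseline.** Unless stated otherwise, SAP 4.2.1 says "baseline measurement is defined as the latest, valid pre-dose assessment available". Protocol 8.2 defines it the same way. SAP 4.8.4, 4.8.5.1 and 4.8.5.2 all tabulate change from that baseline.

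**The concern.** There are three linked problems.

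1. For blood pressure, the content of the summary table depends on which of two adjacent sentences the programmer follows. Blood pressure is named in the safety objective.
2. For laboratory data, the SAP reverses the protocol's choice of record without saying so. SAP 4.11, which covers changes to the planned analysis, does not mention it. Elsewhere in 4.8.4 the SAP does flag a departure (a urinalysis item that was not performed), so silence here is not its general practice.
3. Selecting the worst value after baseline but the latest value at baseline is asymmetric. Where a subject has repeats, the expected change is no longer zero when nothing has changed.

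In addition, *worst* has no stated direction for measures that can be abnormal either way, such as blood pressure, sodium, potassium or heart rate. SAP 4.8.4 itself classifies laboratory values as low, normal or high.

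**Working it through.** **Step 1: set the rules side by side.**

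| Measure | Protocol 8.2 | SAP, measure-specific | SAP baseline (4.2.1) |
|---|---|---|---|
| Laboratory | first valid; unscheduled values listed only | worst valid, post-baseline (4.8.4) | latest valid |
| Blood pressure | unscheduled values listed only | worst record, and repeats excluded (4.8.5.1) | latest valid |
| ECG | no rule on repeats | worst, post-baseline (4.8.5.2) | latest valid |

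The latest-versus-worst mismatch is explicit for laboratory data and ECG. For blood pressure it arises only if the worst-record sentence is followed and the 4.2.1 definition governs at baseline.

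**Step 2: direction of the effect.** The documents give neither repeat rates nor within-subject SDs, so results are in units of the within-subject SD (σ), with assumed repeat rates of 5%, 10% and 20%. There is no true change in any scenario. Worse is taken as higher.

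*Repeats unrelated to the first reading, one unselected baseline reading.* The expected larger of two normal readings is σ/√π = 0.564σ above the subject's mean; of three, 1.5σ/√π = 0.846σ. With two readings, the group-mean shift is the repeat fraction times 0.564:

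- 5%: 0.05 × 0.564 = 0.028σ
- 10%: 0.10 × 0.564 = 0.056σ
- 20%: 0.20 × 0.564 = 0.113σ

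*Repeats triggered by a high reading, at baseline and at follow-up.* Simulation with 2,000,000 subjects, between-subject SD assumed equal to σ, and a second reading taken when the first lies in the top 5%, 10% or 20%. Mean change, in σ:

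| Follow-up rule minus baseline rule | 5% | 10% | 20% |
|---|---|---|---|
| worst minus latest (SAP) | 0.077 | 0.136 | 0.230 |
| first minus latest | 0.074 | 0.125 | 0.199 |
| first minus first | 0.00 | 0.00 | 0.00 |
| latest minus latest | 0.00 | 0.00 | 0.00 |
| worst minus worst | 0.00 | 0.00 | 0.00 |

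**Step 3: locate the cause.** When a high reading triggers the repeat, the first reading is usually already the worst. Taking worst instead of first at follow-up therefore adds little: 0.077 − 0.074 = 0.004 (from unrounded values), 0.136 − 0.125 = 0.011 and 0.230 − 0.199 = 0.031σ. Most of the shift comes from the baseline side, where a high reading is replaced by a recheck that falls back toward the subject's mean. At 20%, 0.199/0.230 = 86% of the shift would remain if only the follow-up rule were changed to first valid. Any rule used at both times removes it.

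**Step 4: contrast between arms.** With random repeats and two readings, the between-arm difference is the difference in repeat rates times 0.564. Equal rates give 0; 20% against 10% gives 0.10 × 0.564 = 0.056σ.

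**The case against.** **The vital-signs sentences can be reconciled.** Multiple records might mean scheduled replicates, and repeated measurements might mean unscheduled rechecks. The SAP does not say so, Protocol 6.2.3 describes no scheduled replicate readings, and SAP 4.2.2 uses the word repeated for the worst-value rule. The contradiction stands.

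**The SAP governs.** SAP 4.2 says analyses follow the SAP, so for laboratory data the programmer has one clear instruction. That is right: the laboratory issue is an undeclared departure from the protocol, not an ambiguity. A reader might infer that first valid, worst and excluded all collide on one measure. They do not; first against worst concerns laboratory data, and worst against excluded concerns vital signs.

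**The consequence is small.** SAP 4.7.1.3 has safety read on clinical grounds without hypothesis testing, the selection acts in every arm, and taking the worst value is a conservative convention for threshold counts. All of this stands. Unequal repeat rates are nevertheless plausible. The trial of another 5-HT₆ antagonist summarised in the Protocol's introduction reported raised GGT in 10% against 2% on placebo and raised ALT in 6% against 0%. One liver criterion in SAP 4.8.4 depends on an elevation lasting more than two weeks, which invites follow-up tests. Whether SUVN-502 would behave the same way is unknown.

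**A figure in mmHg.** A reader might assume a systolic within-subject SD of 5-10 mmHg and 20% repeats, and infer a spurious rise of 0.564 × 5-10 × 0.20 = 0.6-1.1 mmHg. The documents support neither input, and the formula treats repeats as unrelated to the first reading, which does not fit rechecks prompted by abnormal values.

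**Conclusion.** The point holds as a wording and consistency defect of low severity. SAP 4.8.5.1 cannot be executed as written for repeated blood pressures. SAP 4.8.4 departs from Protocol 8.2 undeclared. The worst-value rule paired with a latest-value baseline shifts mean change toward worsening for subjects with repeats in laboratory and ECG tables, and in blood-pressure tables on one reading.

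The illustrative 0.08-0.23σ rests on repeats triggered by high readings in 5-20% of cases and equal between- and within-subject SDs. It shows direction and cause, not the size to expect in this trial. Efficacy analyses are untouched.

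A reader might also infer that restoring the protocol's first-valid rule after baseline is enough. It is not, because both documents keep the latest value at baseline.

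**What to change.** - For mean and change-from-baseline summaries of laboratory data, blood pressure and ECG, apply one selection rule at baseline and at every post-baseline visit, for example the first valid scheduled value at both. SAP 4.2.1 already allows a stated exception to its baseline definition.
- Keep unscheduled values in listings only, as Protocol 8.2 does for laboratory data and vital signs, and say the same for ECG.
- In SAP 4.8.5.1, remove the worst-record sentence for these summaries, and state in 4.2.2 that its worst-value default does not apply to them.
- Use the worst value only for shift and threshold tables, including the liver criteria in SAP 4.8.4. Define the direction for each parameter, with low and high handled separately where both matter.
- State in the SAP any remaining departure from Protocol 8.2, including a safety baseline other than the latest valid value if that option is chosen.

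The cost is SAP wording and minor programming, before database lock. No data collection changes.
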